4. To compare doxycycline concentrations in vaginal tissues collected 24 hours after T⁵ dose (Visit 8) of 100 mg or 200 mg of doxycycline in AFAB participants.

Exploratory Endpoint

To assess longitudinal doxycycline concentrations in blood, urine, throat, vaginal, penile, and rectal secretions over the 3-week study period in people taking 5 doses of 100mg vs. 200mg of doxycycline.

5. Study Intervention/Investigational Agent

Study Product Description

Doxycycline is used to treat or prevent infections that are strongly suspected to be caused by bacteria; it is an antimicrobial drug indicated for bacterial infections such as sexually transmitted infections.

It will be purchased from the manufacturer and stored at the Emory Investigational Drug Services (IDS).

Dosage, Preparation and Administration of Study Product

[figure not shown]
Doxycycline (DOX) will be given orally at 100 and 200 mg doses. Pharmacy packages will be prepared by an IDS Pharmacist and delivered to the participant by a study team member. Prior to drug dispensing, the clinician will assess participant's medical history, and ensure the participant has no known allergies to the study drug. If a participant reports an allergy and a suitable alternative is not available, then the clinician may opt to not enroll the participant into the study.

Accountability Procedures for the Study Product

The IDS pharmacist will maintain accurate accountability logs at the Hope Clinic.

6. Procedures Involved

Study Schema

Study Visits

All study visits described below apply to both Arms A & B. The only difference between the two will be the dose participants receive (100 mg v. 200 mg). Study participants will be assigned to dosing arms in a sequential manner. Arm A will enroll at least 6 participants AFAB and at least 6 participants AMAB at 100mg prior to proceeding to Arm B. Target enrollment will be n=10 in each group. Arm B will enroll at least 6 participants AFAB and at least 6 participants AMAB at 200mg. Target enrollment will be n=10 in each group.

Recruitment

Potential participants will be identified from one of the recruitment methods (e.g., flyers, social media, advertisements, etc.) mentioned in the recruitment methods section below.

Phone Screening

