This visit will take place 24 hours after the first dose (T¹ = 0 hr). For participants who menstruate, this visit should take place 7-10 days after their last menstrual cycle.

Participants will be asked to abstain from receptive anal and/or vaginal intercourse for 3 days prior to this visit.

Procedures conducted at this visit may include:

- Review of medical history
- Review of current medications
- Symptom-guided physical exam
- Evidence-based HIV/STI risk reduction counseling
- Rapid HIV test (if risk behavior has changed since screening)
- Blood Sample Collection – up to 10 mL
- Urine Sample Collection

Protocol Title: Doxy-PEP

- Urinalysis
- Urine pregnancy test – for women of childbearing potential
- Staff-Assisted Swab Collection
 - Urethral (x1)
 - Glans (x1)
- Self-Administered Swab Collection
 - Rectal (x3)
 - Vaginal (x3) – for participants with a vagina only
 - Throat (x2)
- Rectal Biopsy – *Required for participants who DO NOT have a vagina. This is an optional, additional biopsy for those who do have a vagina.*
 - Rigid sigmoidoscopy
 - Biopsies (2-4 tissue samples)
- Vaginal/Cervical Biopsy – *Required for participants who DO have a vagina.*
 - Speculum insertion
 - Vaginal Biopsies (1-2 tissue samples)
 - Cervical Biopsies (1-2 tissues samples)

All participants will be instructed to place nothing in the rectum and/or vagina and to abstain from intercourse for 7 days after the biopsy procedure to allow the mucosa to heal.

Visit 3 (Hour 48/Day 2)

This visit will take place 48 hours after the first dose ($T^1 = 0$ hr).

Procedures conducted at this visit may include:

- Blood Sample Collection – up to 10 mL
- Urine Sample Collection – Urinalysis
- Self-Administered Swab Collection
 - Rectal (x3)
 - Vaginal (x3) – for participants with a vagina only
 - Throat (x2)

Visit 4 (Hour 72/Day 3) – Pre- T^2 Dose & T^2 Dosing

This visit will take place 72 hours (3 days) after the first dose ($T^1 = 0$ hr).

Procedures conducted PRIOR TO DOSING may include:

- Blood Sample Collection – up to 10 mL
- Urine Sample Collection – Urinalysis
- Staff-Assisted Swab Collection
 - Urethral (x1)
 - Glans (x1)
- Self-Administered Swab Collection

Protocol Title: Doxy-PEP

- Rectal (x3)
- Vaginal (x3) – for participants with a vagina only
- Throat (x2)

Dosing

Doxycycline (Arm A – 100mg; Arm B – 200 mg) will be administered to the participant. This dose should take place while the participant is in the clinic.

Visit 5 (Hour 168/Day 7) – T³ Dosing at Home

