Participant will take dose (Arm A – 100mg; Arm B – 200 mg) at home and provide proof of dosing as described in study-specific procedures.

Visit 6 (Hour 240/Day 10) – T⁴ Dosing at Home

Participant will take dose (Arm A – 100mg; Arm B – 200 mg) at home and provide proof of dosing as described in study-specific procedures.

Study Drug Dispensation Visit (if needed)

If, due to scheduling constraints, menses, holidays, etc., Visit 8 (Biopsy) cannot be completed per protocol, study staff may delay Visits 7a – 12 for up to 4 weeks. In this case, participants would continue to take doxycycline twice a week until the visits could be scheduled. An additional drug dispensation visit may be needed so the participant can pick up study drug.

Visit 7a (Hour 336/Day 14) – Pre-Dose & T⁵ Dosing

This visit will take place 336 hours (14 days) after the first dose (T¹ = 0 hr).

Procedures conducted at this visit may include:

- Blood Sample Collection – up to 10 mL
- Urine Sample Collection – Urinalysis
- Self-Administered Swab Collection
 - Rectal (x3)
 - Vaginal (x3) – for participants with a vagina only
 - Throat (x2)

Dosing

Doxycycline (Arm A – 100mg; Arm B – 200 mg) will be administered to the participant. This dose should take place while the participant is in the clinic.

Visit 7b (Hour 338-340/Day 14) – Post-T⁵ Dose

This visit will take place 2-4 hours after the T⁵ dose and 338-340 hours (14 days) after the first dose (T¹ = 0 hr).

Procedures conducted at this visit may include:

- Blood Sample Collection – up to 10 mL
- Self-Administered Swab Collection
 - Rectal (x3)
 - Vaginal (x3) – for participants with a vagina only
 - Throat (x2)

Visit 8 (Hour 360/Day 15) – Biopsy Visit

This visit will take place 360 hours (15 days) after the first dose ($T^1 = 0$ hr) and 24 hours after T^5 dose.

Participants will be asked to abstain from receptive anal and/or vaginal intercourse for 3 days prior to this visit.

- Review of medical history
- Review of current medications
- Symptom-guided physical exam
- Evidence-based HIV/STI risk reduction counseling
- Rapid HIV test (if risk behavior has changed since screening)
- Blood Sample Collection – up to 10 mL
- Urine Sample Collection
 - Urinalysis
 - Urine pregnancy test – for participants who are able to bear children
- Staff-Assisted Swab Collection
 - Urethral (x1)
 - Glans (x1)
- Self-Administered Swab Collection
 - Rectal (x3)
 - Vaginal (x3) – for participants with a vagina only
 - Throat (x2)

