- Rectal Biopsy – *Required for participants who DO NOT have a vagina. This is an optional, additional biopsy for those who do have a vagina.*
 - Rigid sigmoidoscopy
 - Biopsies (8-12 tissue samples)
- Vaginal/Cervical Biopsy – *Required for participants who DO have a vagina.*
 - Speculum insertion
 - Vaginal Biopsies (1-2 tissue samples)
 - Cervical Biopsies (1-2 tissue samples)

All participants will be instructed to place nothing in the rectum and/or vagina and to abstain from sex for 7 days after the biopsy procedure to allow the mucosa to heal.

Visit 9 (Hour 384/Day 16)

This visit will take place 384 hours (16 days) after the first dose ($T^1 = 0$ hr).

Procedures conducted at this visit may include:

- Blood Sample Collection – up to 10 mL
- Urine Sample Collection – Urinalysis
- Self-Administered Swab Collection
 - Rectal (x3)
 - Vaginal (x3) – for participants with a vagina only
 - Throat (x2)

Visit 10 (Hour 408/Day 17)

This visit will take place 408 hours (17 days) after the first dose ($T^1 = 0$ hr).

Procedures conducted at this visit may include:

- Blood Sample Collection – up to 10 mL
- Urine Sample Collection – Urinalysis
- Staff-Assisted Swab Collection
 - Urethral (x1)
 - Glans (x1)
- Self-Administered Swab Collection
 - Rectal (x3)
 - Vaginal (x3) – for participants with a vagina only
 - Throat (x2)

Visit 11 (Hour 432hr/Day 18)

This visit will take place 432 hours (18 days) after the first dose ($T^1 = 0$ hr).

Procedures conducted at this visit may include:

- Blood Sample Collection – up to 10 mL
- Urine Sample Collection – Urinalysis
- Swab Collection
 - Rectal (x3)
 - Vaginal (x3) – for participants with a vagina only
 - Throat (x2)

Visit 12 (Hour 504/Day 21)

This visit will take place 504 hours (21 days) after the first dose ($T^1 = 0$ hr).

Procedures conducted at this visit may include:

- Blood Sample Collection – up to 10 mL
- Urine Sample Collection – Urinalysis
- Swab Collection
 - Rectal (x3)
 - Vaginal (x3) – for participants with a vagina only
 - Throat (x2)

Study-Specific Procedures

Visit Windows

Windows for all study visits are provided in Table 1. Study staff should make efforts to stay within these windows, however, study procedures done outside the provided windows will not be considered a protocol deviation.

Dosing

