Vaginal and cervical tissue samples will not be collected in women who are menstruating, pregnant, or have possible cervical or vaginal infection. A pregnancy test will be administered to women of childbearing potential to ensure they are not pregnant. The first vaginal/cervical biopsy will be scheduled 7 to 10 days after their last menstrual cycle.

Twenty-four to forty-eight hours after the procedure, study personnel will call the participants who donated biopsy samples and inquire about symptoms, complications, or adverse events related to study procedures. Participants who report symptoms suggestive of any significant complications will receive advice on seeking care and will be given referrals to appropriate healthcare professionals as needed. This follow-up may be completed over the phone or through electronic communication.

Rectal Mucosal Sampling Procedures

A trained, delegated clinician will be performing all rectal mucosal sampling procedures with the assistance of the study coordinator utilizing a disposable anoscope, rigid sigmoidoscope, light source, and jumbo biopsy forceps.

Then, without the administration of any previous enemas or other preparation, a rigid sigmoidoscope will be inserted and 2-4 (first biopsy) or 8-12 (second biopsy) adequate ~1.0 mm thick biopsy specimens will be taken from normal-appearing rectal mucosa approximately 10 cm above the external anal aperture using flexible sigmoidoscopic forceps mounted on a semi-flexible rod. All biopsy specimens will be coded with a unique numeric identifier such that the laboratories that receive the specimens will be unable to link them back to the study participants. Two to three biopsy specimens will be placed immediately into cryotubes for testing of drug levels at CDC. The remaining biopsy specimens will be placed in media and transported to [name] lab where the specimens will be processed for various laboratory protocols (e.g., bulk and spatial transcriptomics, exogenous hormone treatment for bulk and spatial transcriptomics and explant challenge experiments, or flash-frozen for subsequent quantification of HIV within rectal tissue).

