Twenty-four to forty-eight hours after the procedure, study personnel will call the participants who donated rectal biopsy samples and inquire about symptoms, complications, or adverse events related to study procedures. Participants who report symptoms suggestive of any significant complications will receive advice on seeking care and will be given referrals to appropriate healthcare professionals as needed. This follow-up may be completed over the phone or through electronic communication.

Protocol Title: Doxy-PEP

Table 1. Study Schema – Arm A & B

	Screening Visit	Visit 1a	Visit 1b	Visit 2	Visit 3	Visit 4	Visit 5	Visit 6	Visit 7a	Visit 7b	Visit 8	Visit 9	Visit 10	Visit 11	Visit 12
Timepoint (Days)	-42 to 0	0	0	1	2	3	7	10	14	14	15	16	17	18	21
Timepoint (Hours)	-	0	2-4	24	48	72	168	240	336	338-340	360	384	408	432	504
Window	-	-	±2 hr	±2 hr	±2hr	±2 hr	±2hr	±2hr	±2hr	±2hr	±2hr	±2hr	±2hr	±72hr	±72hr
Informed Consent	X														
Physical Exam	X			X ¹							X ¹				
Medical History	X			X ¹							X ¹				
Current Medications	X			X ¹							X ¹				
Screening Labs ²	X														
Pregnancy Test	X			X							X				
Eligibility	X														
Dose Administration		X				X	X ³	X ³	X						
Biopsy				X							X				
Urine Sample	X	X		X	X	X			X		X	X	X	X	X
Rectal & Vaginal ⁴ Swab		X	X	X	X	X			X	X	X	X	X	X	X
Throat Swab		X	X	X	X	X			X	X	X	X	X	X	X
Urethral & Glans Swab				X		X					X		X		
Blood Volume	17 mL	10 mL	10 mL	10 mL	10 mL	10 mL			10 mL	10 mL	10 mL	10 mL	10 mL	10 mL	10 mL

¹Abbreviated/symptom-directed/review during non-screening visits.

²Includes CBC, coagulation, creatinine, HIV testing, urine, and self-collected swab for chlamydia & gonorrhea.

³Dose taken at home.

⁴Vaginal swabs done only on participants with vaginas.

7. Statistical Analysis Plan

Primary Outcomes

Comparisons between time points will be conducted with a non-parametric statistical test of differences in median doxycycline concentrations between the two dosing regimen arms, stratified by sex assigned at birth. P-values less than 0.05 will be considered significant.

Exploratory Outcomes

Exploratory outcomes will be analyzed with various statistical methods to examine changes over time in doxycycline concentrations between the dosing arms, stratified by sex assigned at birth.

8. Data and/or Specimen Banking

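### On the decline curves after T1 and T5, all vaginal swabs, and all rectal swabs in participants who had a rectal biopsy, nominally fall 1 to 6 days after biopsy, and Section 7 does not allow for this

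*Combined protocol and SAP*

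**What the plan says.** Section 4 makes the secretion time course an exploratory endpoint, comparing 100 mg with 200 mg: "To assess longitudinal doxycycline concentrations in blood, urine, throat, vaginal, penile, and rectal secretions over the 3-week study period".

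Section 6 sets the schedule. For the first biopsy visit (Visit 2) it says "This visit will take place 24 hours after the first dose". For the second (Visit 8) it says "This visit will take place 360 hours (15 days) after the first dose", which it also describes as 24 hours after T5. Rectal swabs, and vaginal swabs in participants with a vagina, are listed at Visits 1a, 1b, 2, 3, 4, 7a, 7b, 8, 9, 10, 11 and 12.

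Vaginal and cervical biopsy is required in participants with a vagina, at one to two specimens per site on both occasions. Rectal biopsy is required in participants without a vagina; for the others, "This is an optional, additional biopsy for those who do have a vagina". The rectal procedure takes "2-4 (first biopsy) or 8-12 (second biopsy) adequate ~1.0 mm thick biopsy specimens".

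After each biopsy, participants are told to insert nothing at either site for 7 days while the tissue heals. Section 7 analyses the exploratory outcomes with "various statistical methods to examine changes over time in doxycycline concentrations between the dosing arms", stratified by sex assigned at birth. It mentions neither biopsy nor blood on swabs.

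**The concern.** The swabs after 24 h show how long drug persists in secretions. Comparing the profile after T1 with that after T5 bears on accumulation, which Section 3 names as a gap in knowledge. Both readings assume that the fluid on the swab is ordinary mucosal secretion.

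The protocol gives reason to doubt this shortly after a biopsy. Section 17 describes the biopsied rectal surface as damaged and refers to mucosal bleeding. Section 6 allows a haemostatic paste at vaginal and cervical sites, and Section 17 warns that residue may show up in vaginal discharge, which is the fluid being swabbed. Blood is itself one of the matrices in which doxycycline is measured, so blood on a swab changes the reading unless the two concentrations happen to be equal.

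If contamination is not recorded when the swab is taken, its effect cannot be separated from drug decline afterwards.

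**Working it through.** **The plan's own figure.** T5 is given at Visit 7a, for which Section 6 says "This visit will take place 336 hours (14 days) after the first dose". Adding 24 h gives 336 + 24 = 360 h, which agrees with the stated time of Visit 8. The two biopsy times are therefore hours 24 and 360.

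**Time since biopsy.** Inputs are the visit hours in Section 6 and the windows in Table 1 (±2 h for Visits 3, 4, 9 and 10; ±72 h for Visits 11 and 12). Days since biopsy = (swab hour − hour of latest biopsy) / 24. The window is applied to the swab visit only.

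| Visit | Hour | Hours after dose | Days after biopsy (nominal) | Range with window (days) |
|---|---|---|---|---|
| 3 | 48 | 48 after T1 | (48 − 24)/24 = 1 | 0.92 to 1.08 |
| 4 | 72 | 72 after T1 | (72 − 24)/24 = 2 | 1.92 to 2.08 |
| 9 | 384 | 48 after T5 | (384 − 360)/24 = 1 | 0.92 to 1.08 |
| 10 | 408 | 72 after T5 | (408 − 360)/24 = 2 | 1.92 to 2.08 |
| 11 | 432 | 96 after T5 | (432 − 360)/24 = 3 | 0 to 6 |
| 12 | 504 | 168 after T5 | (504 − 360)/24 = 6 | 3 to 9 |

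All six swab visits on the two decline curves fall within 7 days of a biopsy at nominal times. Visit 12 can fall outside 7 days if its window is used. A delay of Visits 7a to 12, which Section 6 permits, moves the whole T5 block together and leaves these intervals unchanged.

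**Visits that are clear of a recent biopsy.** Visits 1a and 1b precede any biopsy. Visit 7a is (336 − 24)/24 = 13.0 days after the first biopsy. Visit 7b, at its midpoint of 339 h, is (339 − 24)/24 = 13.1 days after, and Visit 8 is (360 − 24)/24 = 14.0 days after. Provided the Visit 2 and Visit 8 swabs are taken before that day's biopsy, the pairs 1b with 7b and 2 with 8 allow a T1-versus-T5 comparison at matched times, outside any 7-day healing period.

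**Direction and size.** Let f be the share of blood in the swab fluid and R the ratio of blood to secretion concentration. Then observed/true = 1 + f(R − 1). The reading is too high if R > 1, too low if R < 1, and right if R = 1 or f = 0. The documents give neither f nor R, so no figure for the bias can be derived.

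**Dose contrast.** If f and R are the same in both arms at a given visit, the factor 1 + f(R − 1) cancels from the 200 mg to 100 mg ratio. It does not cancel between visits within an arm if f or R changes with time since biopsy.

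**Unbiopsied reference.** For vaginal swabs, and for rectal swabs in participants without a vagina, the plan requires biopsy of everyone, so biopsy is aliased with time on the decline curves. The only planned unbiopsied site is the rectum of participants with a vagina who decline the optional procedure. That group is self-selected, of unknown size (target 10 AFAB per arm), and lies in one sex stratum.

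**The case against.** The strongest case against is that this is an interpretive caveat on one exploratory endpoint. The planned contrast is between doses, both arms follow the same biopsy schedule, and sex is a stratum, so no rectal comparison between the sexes is planned. Section 17 calls rectal bleeding self-limited. Rectal biopsies are taken about 10 cm above the anal opening and the depth of the self-swab is not given, so a rectal swab may not touch the biopsied area. The case report forms are not in the documents, so it cannot be said that blood goes unrecorded, only that the protocol does not mention it. A biopsy term in a model could not repair the problem, because it is aliased with time or confounded with sex.

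Most of this stands and limits the point. It does not remove the risk to the within-arm decline or to a T1-versus-T5 comparison, and it strengthens the case for recording contamination at collection rather than modelling it later.

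A reader might also infer more from the specimen counts. The rectal count is 8/4 = 2 to 12/2 = 6 times higher at the second biopsy, which suggests heavier bleeding after T5. The documents do not support that: Section 17 says that minor bleeding and pain were unrelated to the number of rectal biopsies. The difference is also rectal only, since vaginal and cervical counts are the same both times.

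**Conclusion.** The concern holds in limited form and is worth fixing before swabs are collected. On the T1 and T5 decline curves, six of six swab visits are nominally 1 to 6 days after biopsy, for all vaginal swabs and for rectal swabs in participants who had a rectal biopsy. This rests on nominal visit times and on biopsies being done as planned. Contamination is a plausible risk, not a documented fact, and its direction and size are unknown.

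A reader might infer that every swab later than 24 h after T1 or T5 comes from a recently biopsied site. That is too broad: Visits 7a and 7b are about 13 days after the first biopsy, Visit 12 can reach day 9 within its window, and participants who decline the optional rectal biopsy give rectal swabs from an unbiopsied rectum. A reader might also infer that the comparison of doses or the primary results are compromised. The shared schedule largely protects the 100 mg versus 200 mg contrast at a given visit, and this point does not bear on the primary tissue endpoints. Blood, urine, throat and penile samples are not affected either.

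**What to change.** 1. Record visible blood or haemostatic residue (yes/no) on the case report form for each rectal and vaginal swab.
2. State in Section 6 that the rectal and vaginal swabs at Visits 2 and 8 are taken before the biopsy. In Section 7, base any T1-versus-T5 comparison of these secretions on the 2-4 h and 24 h swabs (Visits 1b and 2 against 7b and 8).
3. In Section 7, label the decline after 24 h as post-biopsy and repeat that analysis without visibly contaminated swabs. Use rectal swabs from participants with a vagina who declined rectal biopsy only as a descriptive reference, set against biopsied participants in the same sex stratum. Do not use them for a model-based correction.
4. Reconcile the 7-day instruction to insert nothing in the rectum or vagina with the self-administered swabs scheduled in those days.

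The cost is one form field, a stated order of collection and a few lines in Section 7, with no extra samples. The downside is a caveat on the secretion results after 24 h.
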